4.5.9.2 Description of Clinical Outcome Assessment Instruments EORTC QLQ-C30

The EORTC QLQ-C30 (see [Appendix 4](#)) is a validated and reliable self-reported measure (Aaronson et al. 1993; Sprangers et al. 1996; Fitzsimmons et al. 1999). It consists of 30 questions that assess 5 aspects of patient functioning (physical, emotional, role, cognitive, and social), eight symptom scales (fatigue, nausea and vomiting, pain, dyspnea, insomnia, appetite loss, constipation, and diarrhea), financial difficulties, and GHS/HRQoL with a recall period of the previous week.

EORTC QLQ-BR23

The EORTC QLQ-BR23 breast cancer module is meant for use among patients diagnosed with breast cancer (Sprangers et al. 1996). The breast cancer module incorporates five multiple-item scales to assess systemic therapy side effects, arm symptoms, breast symptoms, body image, and sexual functioning. In addition, single items assess sexual enjoyment, hair loss, and future perspective.

BPI-SF “Worst Pain” Item

The BPI-SF is a widely used patient-reported outcome measure for assessing pain, and the “worst pain” item is frequently recommended for evaluating increases in the severity of pain (Cleeland 2009; Shi et al. 2009). The item asks patients to rate their pain at its worst in the last week on a scale from 0 to 10.

PRO-CTCAE

The PRO-CTCAE (see [Appendix 7](#)) is an item bank reflecting 78 symptomatic adverse events rated according to their severity, interference with daily function, frequency, and/or occurrence. The item bank was designed and validated as a repository of standalone items (Basch et al. 2014). PRO-CTCAE will be completed per the schedule of activities (see [Appendix 1](#)), if available in the patient’s preferred language.

Only adverse events that are patient self-reportable (Basch et al. 2014) were selected for assessment in this study. Adverse events that rely on laboratory testing assessments (e.g., neutropenia, anemia) and that may frequently present as being primarily asymptomatic or with nonspecific signs and symptoms were disregarded. Adverse events that did not have an identifiable symptom equivalent in the PRO-CTCAE were also excluded. Based on the above criteria, 7 symptomatic adverse events that have been associated with inavolisib, palbociclib, or fulvestrant treatment were selected from the PRO-CTCAE item bank: diarrhea, nausea, vomiting, decreased appetite, fatigue, mouth sores, and rash symptoms. An additional question providing an overall assessment of the burden of side effects will also be collected.

EQ-5D-5L

The EQ-5D-5L is a validated self-report health status questionnaire that is used to calculate a health status utility score for use in health economic analyses (EuroQol Group 1990; Brooks 1996; Herdman et al. 2011; Janssen et al. 2013). There are two components to the EQ-5D-5L: a five-item health state profile that assesses mobility, self-care, usual activities, pain/discomfort, and anxiety/depression, as well as a VAS that measures health state. Published weighting systems allow for creation of a single composite score of the patient’s health status. The EQ-5D-5L takes approximately 3 minutes to complete. The EQ-5D-5L will be collected to inform pharmacoeconomic modeling and will be included only descriptively in the Clinical Study Report.

4.5.10 Blood Samples for Whole Genome Sequencing (Patients at Participating Sites)

At participating sites (where approved locally), blood samples will be collected for DNA extraction to enable WGS to identify variants that are predictive of response to study treatment, are associated with progression to a more severe disease state, are associated with acquired resistance to study treatment, are associated with susceptibility to developing adverse events, can lead to improved adverse event monitoring or investigation, or can increase the knowledge and understanding of disease biology and

drug safety. Research may aim to distinguish germline mutations from somatic mutations. The samples may be sent to one or more laboratories for analysis. WGS is not applicable in China.

Collection and submission of blood samples for WGS is contingent upon the review and approval of the exploratory research by each site's IRB/EC and, if applicable, an appropriate regulatory body. If a site has not been granted approval for WGS sampling, this section of the protocol (Section 4.5.10) will not be applicable at that site.

Genomics are increasingly informing researchers' understanding of disease pathobiology. WGS provides a comprehensive characterization of the genome and, along with clinical data collected in this study, may increase the opportunity for developing new therapeutic approaches, new methods for monitoring efficacy and safety, and/or new methods for predicting which patients are more likely to respond to a drug or develop adverse events. Data will be analyzed in the context of this study but may also be explored in aggregate with data from other studies. The availability of a larger dataset will assist in identification and characterization of important biomarkers and pathways to support future drug development.

For sampling procedures, storage conditions, and shipment instructions, see the laboratory manual.

Blood samples collected for WGS are to be stored until they are no longer needed or until they are exhausted. However, the storage period will be in accordance with the IRB/EC-approved Informed Consent Form and applicable laws (e.g., health authority requirements).

See Section 4.5.6 for details on use of samples after patient withdrawal, confidentiality standards for data, and availability of data from biomarker analyses.

4.5.11 Optional Tumor Biopsies

Consenting patients will undergo optional tumor biopsies after treatment initiation between Days 15 and 22 (± 1 day) of Cycle 1 and/or at disease progression and may undergo additional on-treatment biopsies at any other time at the investigator's discretion (if deemed clinically feasible by the investigator). Participation in "consent for optional biopsy collection" is not available in China. Samples collected via resection, core needle biopsy (three cores in the same block preferred), or excisional, incisional, punch, or forceps biopsy are preferred. For sampling procedures, storage conditions, and shipment instructions, see the laboratory manual.

The Informed Consent Form will contain a separate section that addresses optional biopsies. A separate, specific signature will be required to document a patient's agreement to undergo optional biopsies. The investigator should document whether or

not the patient has given consent to participate and (if applicable) the date(s) of consent, by completing the Optional Biopsy Sample Informed Consent eCRF.

Samples may be used for exploratory biomarker research as described in Section 4.5.6. See Section 4.5.6 for details on duration of sample storage, use of samples after patient withdrawal, confidentiality standards for data, and availability of data from biomarker analyses.

4.5.12 Optional Samples for Research Biosample Repository

4.5.12.1 Overview of the Research Biosample Repository

The Research Biosample Repository (RBR) is a centrally administered group of facilities used for the long-term storage of human biological specimens, including body fluids, solid tissues, and derivatives thereof (e.g., DNA, RNA, proteins, peptides). The collection, storage, and analysis of RBR samples will facilitate the rational design of new pharmaceutical agents and the development of diagnostic tests, which may allow for individualized drug therapy for patients in the future.

Samples for the RBR will be collected from patients who give specific consent to participate in this optional research. RBR samples will be analyzed to achieve one or more of the following objectives:

- To study the association of biomarkers with efficacy or disease progression
- To identify safety biomarkers that are associated with susceptibility to developing adverse events or can lead to improved adverse event monitoring or investigation
- To increase knowledge and understanding of disease biology and drug safety
- To study drug response, including drug effects and the processes of drug absorption and disposition
- To develop biomarker or diagnostic assays and establish the performance characteristics of these assays

Sites in China are excluded from the “optional samples for research biosample repository” collection.

4.5.12.2 Approval by the Institutional Review Board or Ethics Committee

Collection, storage, and analysis of RBR samples is contingent upon the review and approval of the exploratory research and the RBR portion of the IRB/EC and, if applicable, an appropriate regulatory body. If a site has not been granted approval for RBR sampling, this section of the protocol (Section 4.5.12) will not be applicable at that site.

4.5.12.3 Sample Collection

The following samples will be stored in the RBR and used for research purposes, including, but not limited to, research on biomarkers related to inavolisib, cancer, diseases, or drug safety:

- Leftover blood, serum, plasma, and tumor tissue samples (with the exception of remaining archival tissue blocks, which will be returned to sites) and any derivatives thereof (e.g., DNA, RNA, proteins, peptides), including leftover blood and tumor tissue samples from medically indicated procedures performed at the investigator's discretion during the course of the study

The above samples may be sent to one or more laboratories for analysis of germline or somatic variants via WGS, WES, or other genomic analysis methods. Genomics is increasingly informing researchers' understanding of disease pathobiology. WGS and WES provide a comprehensive characterization of the genome and exome, respectively, and, along with clinical data collected in this study, may increase the opportunity for developing new therapeutic approaches or new methods for monitoring efficacy and safety or predicting which patients are more likely to respond to a drug or develop adverse events.

Data generated from RBR samples will be analyzed in the context of this study but may also be explored in aggregate with data from other studies. The availability of a larger dataset will assist in identification and characterization of important biomarkers and pathways to support future drug development.

For sampling procedures, storage conditions, and shipment instructions, see the laboratory manual.

Research Biosample Repository samples are to be stored until they are no longer needed or until they are exhausted. However, the RBR storage period will be in accordance with the IRB/EC-approved Informed Consent Form and applicable laws (e.g., health authority requirements).

4.5.12.4 Confidentiality

Research Biosample Repository samples and associated data will be labeled with a unique patient identification number.

Patient medical information associated with RBR samples is confidential and may be disclosed to third parties only as permitted by the Informed Consent Form (or separate authorization for use and disclosure of personal health information) signed by the patient, unless permitted or required by law.

Given the complexity and exploratory nature of the analyses of RBR samples, data derived from these analyses will generally not be provided to study investigators or patients unless required by law. The aggregate results of any conducted research will

be available in accordance with the effective Sponsor policy *in the* study data publication.

Data generated from RBR samples must be available for inspection upon request by representatives of national and local health authorities, and Sponsor monitors, representatives, and collaborators, as appropriate.

Any inventions and resulting patents, improvements, and/or know-how originating from the use of the RBR data will become and remain the exclusive and unburdened property of the Sponsor, except where agreed otherwise.

4.5.12.5 Consent to Participate in the Research Biosample Repository

The Informed Consent Form will contain a separate section that addresses participation in the RBR. The investigator or authorized designee will explain to each patient the objectives, methods, and potential hazards of participation in the RBR. Patients will be told that they are free to refuse to participate and may withdraw their consent at any time and for any reason during the storage period. A separate, specific signature will be required to document a patient's agreement to provide optional RBR samples. Patients who decline to participate will not provide a separate signature.

The investigator should document whether or not the patient has given consent to participate and (if applicable) the date(s) of consent, by completing the RBR Research Sample Informed Consent eCRF.

In the event of an RBR participant's death or loss of competence, the participant's samples and data will continue to be used as part of the RBR research.

4.5.12.6 Withdrawal from the Research Biosample Repository

Patients who give consent to provide RBR samples have the right to withdraw their consent at any time for any reason. After withdrawal of consent, any remaining samples will be destroyed or will no longer be linked to the patient. However, if RBR samples have been tested prior to withdrawal of consent, results from those tests will remain as part of the overall research data. If a patient wishes to withdraw consent to the testing of his or her RBR samples during the study, the investigator must inform the Medical Monitor in writing of the patient's wishes through use of the appropriate RBR Subject Withdrawal Form and must enter the date of withdrawal on the RBR Research Sample Withdrawal of Informed Consent eCRF. If a patient wishes to withdraw consent to the testing of his or her RBR samples after closure of the site, the investigator must inform the Sponsor by emailing the study number and patient number to the following email address:

[contact]

A patient's withdrawal from this study does not, by itself, constitute withdrawal of consent for testing of RBR samples. Likewise, a patient's withdrawal of consent for testing of RBR samples does not constitute withdrawal from this study.

4.5.12.7 Monitoring and Oversight

Research Biosample Repository samples will be tracked in a manner consistent with Good Clinical Practice by a quality-controlled, auditable, and appropriately validated laboratory information management system, to ensure compliance with data confidentiality as well as adherence to authorized use of samples as specified in this protocol and in the Informed Consent Form. Sponsor monitors and auditors will have direct access to appropriate parts of records relating to patient participation in the RBR for the purposes of verifying the data provided to the Sponsor. The site will permit monitoring, audits, IRB/EC review, and health authority inspections by providing direct access to source data and documents related to the RBR samples.

4.6 TREATMENT, PATIENT, STUDY, AND SITE DISCONTINUATION

4.6.1 Study Treatment Discontinuation

Patients must permanently discontinue study treatment if they experience any of the following:

- Any medical condition that the investigator or Sponsor determines may jeopardize the patient's safety if she or he continues to receive study treatment
- Investigator or Sponsor determination that treatment discontinuation is in the best interest of the patient
- Intolerable toxicity related to study treatment determined by the investigator to be unacceptable given the potential for treatment benefit and the severity of the event
- Unequivocal disease progression per investigator assessment according to RECIST v1.1
- Symptomatic deterioration attributed to disease progression
- Non-compliance with protocol-specified drug administration and follow-up tests
- Concomitant use of any other (non-protocol) systemic anti-cancer therapy
- Pregnancy

The primary reason for study treatment discontinuation should be documented on the appropriate eCRF. Patients who discontinue study treatment will not be replaced.

All patients will return to the clinic for a safety follow-up visit 30 (± 7) days after the final dose of study treatment (see [Appendix 1](#) for additional details).

Discontinuation from final study treatment is not discontinuation from the study. After treatment discontinuation, information on survival follow-up and new anti-cancer therapy will be collected via telephone calls, patient medical records, and/or clinic visits, approximately every 3 months until death, unless the patient withdraws consent or the

Sponsor terminates the study. Patients that discontinue study treatment for reasons other than objective disease progression, withdrawal of consent, or death will continue to have tumor assessments performed every 8 weeks (± 7 days) for the first 2 years after randomization and then every 12 weeks (± 7 days) until documented disease progression or onset of new anti-cancer therapy, whichever occurs first.

4.6.2 Patient Discontinuation from the Study

Patients have the right to voluntarily withdraw from the study at any time for any reason. In addition, the investigator has the right to withdraw a patient from the study at any time.

Reasons for withdrawal from the study may include, but are not limited to, the following:

- Patient withdrawal of consent
- Loss to follow-up
- Patient non-compliance, defined as failure to comply with protocol requirements as determined by the investigator or Sponsor
- Study termination or site closure

Note that all patients are to be followed for survival following the discontinuation of study treatment, except in the cases noted above.

Every effort should be made to obtain a reason for patient discontinuation from the study. The primary reason for discontinuation from the study should be documented on the appropriate eCRF. Patients will not be followed for any reason after consent has been withdrawn. Patients who withdraw from the study will not be replaced.

If a patient withdraws from the study, the study staff may use a public information source (e.g., county records, published obituaries, etc.), in accordance with local regulations, to obtain information about survival status.

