4.6.4 Site Discontinuation

The Sponsor has the right to close a site at any time. Reasons for closing a site may include, but are not limited to, the following:

- Excessively slow recruitment

- Poor protocol adherence
- Inaccurate or incomplete data recording
- Non-compliance with the International Council for Harmonisation (ICH) guideline for Good Clinical Practice
- No study activity (i.e., all patients have completed the study and all obligations have been fulfilled)

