4.3.1 Key Secondary Endpoint

4.3.1.1 Overall Survival

The secondary comparison of interest is the hazard ratio of OS.

OS is defined as the time from randomization to death from any cause. Data for patients who are alive at the time of the analysis data cutoff will be censored at the last date they

were known to be alive. Data from patients without post-baseline information will be censored at the date of randomization.

Analysis methodology is as outlined for the primary endpoint, PFS.

An interim analysis of OS will be performed at the time of the primary analysis of PFS. In addition to the fixed sequence testing approach described before, a group-sequential design (Lan-DeMets with O'Brien-Fleming stopping boundaries) will be used to control the overall type I error rate ([Lan and DeMets 1983](#)) for the OS interim analysis and a final (event-driven, after approximately 153 OS events) analysis of OS.

The median OS in the control arm is assumed to be 35 months and the median OS in the experimental treatment arm is assumed to be 50 months, equating to a hazard ratio of 0.7. At the time of the primary PFS analysis, on the basis of the above assumptions, 105 OS events are expected to have occurred and 153 OS events for the final analysis of OS are expected to have occurred 19 months later. With the above assumptions, the cumulative power at the interim and final OS analysis is 25% and 59%, respectively. This statistical analysis plan for OS has been designed to provide appropriate OS information and maturity to support the primary PFS endpoint. However, if appropriate, additional exploratory analyses of OS may be conducted after the final analysis at time points defined through study milestones such as Health Authority interactions.

Following the estimand framework ([ICH 2020](#)), the attributes of the estimand for the secondary endpoint are defined as follows:

- **Population:** As defined for the primary estimand in Section [4.2.1](#)
- **Variable:** OS defined as time from randomization to death from any cause.
- **Treatment:** As defined for the primary estimand in Section [4.2.1](#)
- **Intercurrent events and Handling strategy:**
 - Start of non-protocol anticancer therapy prior to OS. Following treatment policy, the ICE will be ignored.
 - Early discontinuation from study treatment for any reason prior to an OS event. Following treatment policy, the ICE will be ignored.
- **Population-level summary:** Hazard ratio for OS.

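### Protocol 4.6.2 takes consenting patients withdrawn for non-compliance or site closure out of survival follow-up, in conflict with 4.6.1, 3.1.1 and the treatment-policy estimands; the size of any bias cannot be read from the documents

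*Protocol*

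**What the plan says.** Protocol 4.6.2 states that "the investigator has the right to withdraw a patient from the study at any time". Its list of possible reasons for withdrawal has four entries: withdrawal of consent, loss to follow-up, "Patient non-compliance, defined as failure to comply with protocol requirements as determined by the investigator or Sponsor", and "Study termination or site closure". It then closes with "Note that all patients are to be followed for survival following the discontinuation of study treatment, except in the cases noted above". The section also bars any follow-up once consent is withdrawn, and it lets site staff consult public sources for the survival status of withdrawn patients where local rules permit.

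Protocol 4.6.1 lists "Non-compliance with protocol-specified drug administration and follow-up tests" among the reasons for stopping study treatment. It says that stopping treatment is not leaving the study, and it continues survival contact "approximately every 3 months until death, unless the patient withdraws consent" or the Sponsor ends the study. Tumor assessments go on until progression or new anti-cancer therapy, unless the reason for stopping was progression, withdrawal of consent or death.

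Protocol 4.6.4 allows a site to be closed for reasons that include "Excessively slow recruitment". It does not say what happens to patients already enrolled there.

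SAP 4.3.1.1 treats stopping treatment as an intercurrent event for OS: "Early discontinuation from study treatment for any reason prior to an OS event. Following treatment policy, the ICE will be ignored". SAP 4.2.1 takes the same approach for PFS and includes scans taken after the event.

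**The concern.** The same behaviour by a patient who still consents has two outcomes. Under 4.6.1 a non-compliant patient stops treatment and is followed to death. Under 4.6.2 the same patient may be withdrawn from the study, and the closing note then releases the site from survival follow-up. Nothing tells a site which section applies.

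PFS and OS are analysed in all randomized patients, with treatment discontinuation ignored. That needs data collected after discontinuation. If a protocol rule ends collection for a patient who has not refused it, the endpoint is censored without need. Non-compliance may follow toxicity, which can differ between arms, or declining health, which predicts death. Censoring at that point could then be informative and could move the hazard ratio in either direction. Deaths are also lost from an OS analysis whose stated power is only 59%.

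**Working it through.** **1. The follow-up rules side by side.**

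| Place | What ends survival follow-up | Non-compliance or site closure an exception? |
|---|---|---|
| Protocol 3.1.1 and synopsis | Death, loss to follow-up, consent withdrawal, study termination | No |
| Protocol 4.6.1 | Death, consent withdrawal, study termination | No; non-compliance stops treatment only |
| Appendix 1, survival footnotes | Same four as 3.1.1 | No |
| Protocol 4.6.2 | Any listed reason for withdrawal | Yes, both |

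Only 4.6.2 differs. It already has its own sentence for withdrawal of consent, so the wide exception is not needed to protect that right.

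**2. What happens in the analysis.** OS is censored at the last date known alive (Protocol 6.4.2.1, SAP 4.3.1.1). PFS is censored at the last tumor assessment (SAP 4.2.2). The missed-assessment sensitivity analysis in SAP 4.2.3 acts only when progression is later observed, so it does not reach a patient who has left the study. No OS sensitivity analysis is planned.

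**3. The plan's own figures.** None is disputed. PFS events by Schoenfeld: 4(1.960 + 1.036)² / (ln 0.65)² = 193.5, rounded up to 194 as stated. OS power with boundaries 0.0132 and 0.0460 at 105 and 153 deaths and HR 0.7, by simulation: 25.7% and 59.1% (stated 25% and 59%).

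**4. Illustrative size.** From the documents: 160 patients per arm, uniform accrual over 43 months, OS medians 35 and 50 months, PFS HR 0.65 with a control median of 11 months, cutoffs at month 69 (OS) and month 50 (PFS). Assumed, because the documents are silent: the withdrawal percentages, withdrawal spread evenly over about the first 12 months, the hazard multiplier after withdrawal, exponential times and no other dropout. In each cell the first figure is the HR with full follow-up, which is what a treatment-policy estimand targets. The second is the HR with censoring at withdrawal.

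| Withdrawn, inavolisib / control | Hazard after withdrawal | OS HR | PFS HR |
|---|---|---|---|
| 5% / 5%, 10% / 5% or 10% / 0% | unchanged | 0.701, 0.701 | 0.651, 0.651 |
| 5% / 5% | doubled | 0.703, 0.701 | 0.653, 0.651 |
| 5% / 2% | doubled | 0.721, 0.707 | not run |
| 10% / 3% | doubled | 0.733, 0.700 | not run |
| 10% / 3% | tripled | 0.753, 0.700 | not run |
| 10% / 5% | doubled | 0.725, 0.701 | 0.668, 0.651 |
| 10% / 5% | tripled | 0.742, 0.701 | 0.678, 0.651 |

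The 10% / 3% case with doubled hazard takes 0.10 × 160 = 16 and 0.03 × 160 = 4.8 patients out of follow-up, and deaths fall from 176 to 163. Repeating it with analysis at 153 deaths gives 0.730 and 0.698. Reversing the arms (3% / 10%) in that event-driven run gives 0.673 and 0.699, a bias against inavolisib. With no change in hazard there is no bias, but the 10% / 3% loss delays the 153rd death by about 3 months.

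**5. Site closure.** 320 / 200 = 1.6 patients per site on average. This says nothing about how many patients sit at sites that would be closed.

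**The case against.** The best defence is that 4.6.2 is permissive. It gives possible reasons for withdrawal and requires none. For a patient who stops taking tablets, 4.6.1 is the more specific rule, and a site working from Appendix 1 would keep that patient in follow-up. Section 4.6.2 also offers public records as a route to survival status. All of this is correct. It means the note does not remove non-compliant patients as a matter of course. The conflict remains once a patient is withdrawn under 4.6.2: the exception then applies as written, the records check is optional and subject to local rules, and it supplies nothing for PFS.

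A second objection is that the 4.6.2 note speaks only of survival. That also stands. The loss of scans is an inference from leaving the study, not a stated rule.

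A third is that every input that creates bias is assumed. The documents give no non-compliance rate, no difference between arms and no hazard after withdrawal. Equal withdrawal gives almost nothing, and the opposite imbalance reverses the sign. This limits the figures above to illustration.

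A reader might infer from the table that censoring could carry OS across its final boundary of HR 0.724. The documents do not support that. The boundary belongs to 153 deaths: exp(−2 × 1.995 / √153) = 0.724. The month-69 runs have about 176 deaths under full follow-up, where the same nominal p-value gives exp(−2 × 1.995 / √176) = 0.740, and 0.733 is already inside that. The shift is also small against the noise of one trial: ln(0.733 / 0.700) = 0.046, against a standard error of about 2 / √176 = 0.15, or roughly 0.3 of a standard error.

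A reader might also treat site closure as informative censoring. Nothing suggests that closure would differ by arm in a blinded 1:1 trial or depend on an individual's prognosis.

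**Conclusion.** The conflict is in the current text and should be resolved. Protocol 4.6.2 allows survival follow-up to end for consenting patients whom 4.6.1, 3.1.1 and Appendix 1 keep, and whose later data the treatment-policy estimands need. OS would be censored at the last date known alive unless public records add to it. PFS would probably be censored at the last scan.

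The size is not known. It is negligible if withdrawal is balanced or unrelated to prognosis, and about 0.03 on the OS hazard ratio if 10% versus 3% are withdrawn in the first year and the hazard then doubles. That figure rests on assumed rates, exponential times, no other dropout and no recovery of deaths from public records. No claim about crossing the OS boundary follows. For site closure the expected harm is fewer events, not bias.

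**What to change.** In 4.6.2, limit the exception to withdrawal of consent, loss to follow-up and study termination, which matches 3.1.1 and Appendix 1. State that consenting patients who are non-compliant, or whose site closes, stay in survival follow-up by telephone, records or transfer to another site and, where feasible, in tumor assessments as 4.6.1 describes. Add a cross-reference from 4.6.4 so that closing a site has a stated consequence for patients already enrolled. The rules for stopping treatment need not change.

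The cost is a few sentences in an amendment. Contact by telephone and medical records already exists in 4.6.1, so the downside is a little extra follow-up work for a few patients. No patient who withdraws consent is affected.
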